We expect that 10-20% of patients will stop taking guanabenz before the end of the treatment. We expect that 10-20% of all patients will drop out of the study before assessment of the primary outcome is complete. We will report the number and percentage of GBZ participants who stop taking the allocated medication before the end of the treatment, or drop out before assessment of the primary outcome is complete. We will also report the median and interquartile range of number of weeks actually spent in follow-up and present line listings of the reasons for withdrawal or loss to follow-up".

5.5. Which baseline characteristics of participants will be presented?

- * Median age at baseline in years and months
- * Median age of onset in years and months
- * Median disease duration at baseline in years and months
- * Disease severity score/HUI score at baseline
- * Number of participants with loss of walking without support
- * Median age of loss of walking without support
- * Sex
- * Country of residence

An overview of all gene variants of the GBZ participants and historical controls will be added in a supplementary table.

5.6. How will the baseline characteristics be summarized?

Categorical baseline characteristics will be summarized by presenting the number and percentage in each category. Continuous, normally distributed variables will be summarized by presenting the mean and standard deviation. Continuous, non-normally distributed variables will be summarized by presenting the median and interquartile range. Differences between groups will not be statistically tested, as the historical controls have been matched to the inclusion/exclusion criteria of the guanabenz treated participants.

Section 6. Analysis.

6.1. How are the outcomes of this study defined?

The primary safety outcome is: All adverse events and serious adverse events collected from the start of study treatment until the end of the study and will be summarized for descriptive purposes.

The primary efficacy outcome is the time of loss of ambulation. Loss of ambulation is defined by the loss of walking with support.

The secondary efficacy outcomes are overall survival, HUI attributes and multiscores. Scores on the Vineland, GMFCS-MLD, ELFC-MLD, GMFM, LIPS, GMFCS, MACS CFCS and EDACS will be considered for descriptive purposes.

Other secondary outcomes are Guanabenz PK/PD parameters in plasma and will be summarized for descriptive purposes. Guanabenz exposure will also be correlated with clinical outcome measures.

For more information, please refer to pages 28 to 32 of the study protocol

6.2. Will any calculations or transformations be used to derive any outcome from the original data?

Disease duration will be calculated from age of onset until date of inclusion, screening, baseline, first day of dosing, end of titration, and visits. Ages will be calculated from the date of birth until date of inclusion, screening, baseline, first day of dosing, end of titration, and visits. Time to loss of walking, with or without support, will be calculated from the day of inclusion until the occurrence of the event.

HUI decision tables are used to generate HUI2 and HUI3 single-attribute utility scores, and applied coding algorithms to obtain overall HUI3 Health Index scores. Overall scores on the Vineland and LIPS will be calculated based on their respective domain scores.

6.3. What analysis method will be used and how will the treatment effects be presented?

For the primary efficacy outcome time to loss of ambulation, a comparison of the guanabenz-treated patients will be made with natural history data, adjusting for calendar year of symptoms onset.

For time to loss of ambulation, patients treated with Guanabenz will be matched to historical controls with a 1:2 matching ratio. The matching criteria are:

- Age of symptoms onset
- Degree of handicap regarding ambulation at comparable disease duration

Other variables might be added if considered crucial.

Primary analysis of the primary efficacy endpoint

In the primary analysis, treated patients will be compared to their matched historical controls. We will analyze time to loss of ambulation using the Kaplan-Meier method and the log-rank test, considering the presence of clustered data. Next, the Cox proportional hazards model will be used to provide an estimate of the effect size, which will contain treatment and will be adjusted for calendar year of symptoms onset. The effects size will be reported using the Hazard Ratio (HR). We will take matching into account when estimating standard errors.

Secondary analysis of the primary efficacy endpoint

In the secondary analysis, we will use historical controls with different matching procedures and different matching ratios. We will use the Kaplan-Meier method and the log-rank test, considering the presence of clustered data. The Cox model will contain treatment and will be adjusted for calendar year of symptoms onset, reporting the effects size using the Hazard Ratio (HR).

Analysis of secondary efficacy endpoints.

The same methods that we used for the primary analysis will be used for overall survival. The HUI scores will be analyzed using linear mixed models adjusting for treatment and calendar year of age of onset. A population pharmacokinetic model will be used to assess the drug exposure (such as AUC or concentration at steady state) and this will then be used to assess the relationship with clinical outcomes using correlation or regression methods.

Descriptive analysis for primary and secondary safety endpoints

A listing of all adverse and serious adverse events will be presented for the guanabenz-treated participants, including the corresponding date and time of collection.

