3.1. What is the study design?

This is an open-label, non-randomized study with a historical control group. All patients enrolled will receive guanabenz at their highest tolerated dose, with a target dose of 2 mg/kg/day, a minimum dose of 1 mg/kg/day, and a maximum dose of 10 mg/kg/day. Guanabenz will be administered as oral capsules once daily before bedtime and in addition to the patient's usual standard of care. The control group consists of historical VWM patients collected from an international longitudinal VWM registry with data collection over 20 years, investigating the natural disease course of VWM.

For more details see pages 41 to 50 of the protocol.

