3.6. When will the final statistical analysis of the study data be performed?

The statistical analysis of the primary and secondary endpoints assessed during the hospital stay will be conducted after the last patient has been discharged and the database has been closed (scheduled for July 16, 2025). This will occur approximately one year after the final participants were enrolled, as inclusion ended on May 31, 2024. The current estimate is that these statistical analyses will be performed in August and September 2025.

3.7. At which time points are the outcomes measured and which "windows" are allowed?

The time points of the visits are presented in Table 3 on page 71 of the protocol. As stated on page 71, all visits have a visit window of 14 days before and after the nominal time points, except for visits M0, M12, M24, M36, M48, which have a visit window of 28 days before and after the nominal time points. As indicated on page 71, the end of study visit has to be in the last 6 months before the end of study on May 31, 2025.

Section 4. Statistical Principles.

4.1. Which level or levels of statistical significance will be used in the study?

Primary and secondary efficacy outcomes will be considered significantly different between guanabenz treated participants and historical controls if the one-sided p-values are less than 0.05.

4.2. Will the analysis adjust for multiplicity of statistical testing to ensure control of type I error rate?

As there is one primary efficacy endpoint (loss of ambulation), the analysis will not adjust for multiplicity of statistical testing. Secondary (and other exploratory) endpoints are considered as exploratory.

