4.4. How is compliance defined and assessed?

Compliance is defined as the proportion of prescribed doses actually taken by each patient. Pill-count based compliance is assessed by counting the number of left-over pills in the tablet container and dividing this number by the total number of doses in the treatment regime. Additionally, blood levels of guanabenz are monitored every three months to assess medication adherence. Low outliers will be investigated, as they may indicate non-compliance.

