6.5. Will sensitivity analyses be performed?

For the primary analysis, we will conduct a sensitivity analysis by using different ratios of matching for guanabenz-treated participants and historical controls or weighted matching. For the secondary analysis, we will conduct a sensitivity analysis by using different trimmed weights Parametric models will also be used as an alternative to the Cox model.

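### The SAP fixes no common way of dating loss of walking with support in treated children and registry controls, and plans no analysis for losses known only to lie between two contacts, so the hazard ratio can move from 1 without a drug effect.

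*SAP*

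**What the plan says.** **Endpoint (6.1).** "Loss of ambulation is defined by the loss of walking with support". This is the sole primary efficacy endpoint.

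**Event time (6.2).** "Time to loss of walking, with or without support, will be calculated from the day of inclusion until the occurrence of the event". The rule runs to the occurrence, but says nothing on how the date of occurrence is found in either group.

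**Treated children (3.7).** The section on when outcomes are measured answers with the visit schedule: "all visits have a visit window of 14 days before and after the nominal time points", widened to 28 days for the baseline and yearly visits.

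**Controls (3.1).** They come from an "international longitudinal VWM registry with data collection over 20 years". No contact schedule is given. Under 5.2 a control's walking ability may be judged from a Health Utility Index ambulation score, which records status at one contact and not a date of loss.

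**Analysis (6.3, 6.5).** The primary analysis reads "We will analyze time to loss of ambulation using the Kaplan-Meier method and the log-rank test, considering the presence of clustered data", followed by a Cox model. The sensitivity analyses vary matching ratios and weights, and add: "Parametric models will also be used as an alternative to the Cox model". The form of these models, and the data they would be fitted to, are not stated.

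**Incomplete dates (6.7).** Apart from a missing day of diagnosis, incomplete historical dates are not imputed.

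**The concern.** Randomised arms normally share one process for finding and dating events, so errors in dating largely cancel. Here the control group is external and the two groups have different data sources. A loss of walking between two contacts is known only to lie between the last contact at which the child could walk with support and the first at which the child could not. Kaplan-Meier, log-rank and Cox need a single date. If that date is the detecting contact, the group seen less often has its losses dated later and appears to do better.

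Two consequences are possible. If control dates are close to exact, for example reported by the family, and treated losses are dated at visits, an inactive drug looks mildly protective. If controls are contacted less often than treated children, a real benefit is diluted in a trial of at most 40 treated children (3.3). Changing the matching ratio or the weights draws on the same registry, so it neither reveals nor removes the effect. A control with only a partial date of loss also has no defined event time under 6.7.

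**Working it through.** The SAP states no hazard ratio, event count or contact interval, so there is no figure of its own on this point to reproduce. The check asks how far the Cox hazard ratio moves when the true value is 1.

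**Inputs**
- Loss at 2 years: 30-50%, the complement of the 50-70% in 3.3. That figure is for being alive and walking without support, so it only stands in for the primary endpoint.
- Exponential event times with hazard λ = -ln(S)/2, where S is the event-free proportion at 2 years. S = 0.50 gives 0.693/2 = 0.347 per year; S = 0.60 gives 0.511/2 = 0.255; S = 0.70 gives 0.357/2 = 0.178.
- Follow-up: uniform from 1 to 4 years (first inclusion expected 31 May 2021 in 1.4, inclusion closed 31 May 2024 in 3.6, study end 31 May 2025 in 3.7).
- Treated contact: every 3 months. This is an assumption, taken from 4.4, where "blood levels of guanabenz are monitored every three months to assess medication adherence". The visit table is not in the SAP.
- Control dating: exact, or contact every 3, 6 or 12 months. All are assumptions.

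**Mechanism.** Dating at detection delays an event by about half the interval: 3/2 = 1.5 months in treated children, against 0 (exact), 6/2 = 3 or 12/2 = 6 months in controls. The group with the longer delay accrues extra time at risk, and some of its losses fall beyond the end of follow-up.

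**Simulation.** The same λ in both groups, 200,000 children per group, events dated at the first contact after they occur, Cox model with Efron ties, no matching or clustering. Values are rounded ranges over S = 0.50-0.70 and repeated runs.

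| Control dating (treated 3-monthly) | Event-free censored at end of follow-up | Event-free censored at last contact |
|---|---|---|
| Exact | 0.92-0.96 | 0.94-0.97 |
| Every 3 months | 0.99-1.01 | about 1.00 |
| Every 6 months | 1.06-1.09 | 1.04-1.08 |
| Every 12 months | 1.23-1.29 | 1.12-1.18 |

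With end-of-follow-up censoring and yearly control contact, a true hazard ratio of 0.50 appears as about 0.6 (0.50 × 1.25 = 0.63).

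**Error rate.** With 30 treated and 60 controls (the 1:2 ratio) and a one-sided 5% test, rejection under the null is about 4% with equal 3-monthly contact and 0.5-1.5% with yearly control contact. It is roughly 6-8% with exact control dates, from only 600 trials and so imprecise.

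**With the remedy.** An interval-censored exponential likelihood returns null hazard ratios of 0.99-1.01 at every pair of intervals tried. An interval-censored Weibull model gives 0.98-1.01, and recovers a true 0.50 as 0.49-0.52. The simulated data were exponential, a special case of the Weibull, so this shows that the interval likelihood removes the dating artefact. It does not show robustness to a wrong distribution.

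**The case against.** A reader might infer that treated losses are dated at visits and control losses at registry contacts, so that the primary hazard ratio is biased. The SAP does not support that. Section 6.2 runs the clock "until the occurrence of the event", not until the visit or record that shows it. Sections 5.1 and 5.5 report ages at loss of walking for children before trial follow-up, and 6.7 speaks of historical dates, which suggests that losses are recorded as dated milestones. If the true date is recorded in both groups, the hazard ratio stays at 1 whatever the contact intervals. A dating rule may also stand in the protocol or in the data derivation plan cited in 7.2. All of this stands, and it makes the bias conditional.

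A reader might also infer that the artefact would mainly favour the drug. The larger shifts run the other way: sparser control contact pushes the hazard ratio above 1 and lowers the false-positive rate. Seeing treated children yearly and controls 3-monthly would raise the one-sided error to 12-17%, but nothing in the SAP suggests that pattern.

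The smaller shifts are also modest beside sampling error. With 30 treated and 60 controls the standard error of the log hazard ratio is about 0.3-0.4. Under last-contact censoring, the exact-date and 6-monthly shifts are then roughly 0.1-0.25 standard errors.

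What does not fall is the gap itself. Deriving the event time is the purpose of 6.2, the two groups have different sources, and nothing in the SAP's planned analyses would show whether their dates are comparable.

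**Conclusion.** The point holds in conditional form. The SAP does not establish the date of loss in the same way in both groups, and plans no analysis that allows for events known only to lie between two contacts. If dates come from contacts and the intervals differ, the null hazard ratio lies at about 0.92-0.97 with exact control dates, 1.04-1.09 with 6-monthly and 1.12-1.29 with yearly control contact, depending on the censoring rule.

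These sizes rest on an assumed 3-monthly treated schedule, assumed control intervals, exponential event times, an event rate borrowed from walking without support, and no matching. They show that the effect can be material, not that it is present. Because this is the only primary efficacy endpoint of an externally controlled trial and the safeguard is cheap, the change is worth making before the analysis.

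**What to change.** **In 6.2:** for every child in both groups, derive the date last known able and the date first known unable to walk with support, by the same rule. Set the two equal where the date of loss is truly known. Censor event-free children at the last contact with known walking status. A partial historical date then becomes an interval and needs no imputation.

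**In 6.5:** state that the planned parametric model (for example Weibull) will be fitted to these intervals as interval-censored data, with treatment, calendar year of onset and matched-set clustering. Report it as a sensitivity analysis beside the Cox hazard ratio. If the dates prove exact, the two estimates should broadly agree.

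**Cost:** SAP wording, one more derived date per child and one model in R, with a slightly wider confidence interval for that estimate. The effort is larger if the registry does not readily hold a last-known-able date, which the SAP does not reveal. No design change, extra visit or extra patient is needed.

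### SAP 6.3 calls the primary comparison adjusted for calendar year of onset, but the only test it names is unadjusted, and 4.1 does not say which p-value decides

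*SAP*

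**What the plan says.** SAP 6.3 opens the primary efficacy analysis by promising "a comparison of the guanabenz-treated patients will be made with natural history data, adjusting for calendar year of symptoms onset". Under its heading for the primary analysis it then says: "We will analyze time to loss of ambulation using the Kaplan-Meier method and the log-rank test, considering the presence of clustered data". No calendar-year stratum or covariate is attached to that test. The next sentence begins "Next, the Cox proportional hazards model will be used to provide an estimate of the effect size", and it is this model "which will contain treatment and will be adjusted for calendar year of symptoms onset". Matching is to be reflected in the standard errors.

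SAP 4.1 calls an efficacy outcome significantly different between treated participants and "historical controls if the one-sided p-values are less than 0.05". It does not name the test.

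On the controls, 6.3 states that "patients treated with Guanabenz will be matched to historical controls with a 1:2 matching ratio". It lists two matching criteria: "Age of symptoms onset" and the degree of ambulatory handicap at comparable disease duration. Other variables may be added, but none is named. Section 3.1 describes the source as an "international longitudinal VWM registry with data collection over 20 years". Section 5.2 limits controls to periods in which the disease course is comparable, without giving calendar years or a criterion.

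**The concern.** Allowing for clustering corrects the variance of a log-rank test. It does not remove confounding by calendar year. The text therefore promises an adjusted comparison, names an unadjusted test, and gives the adjusted model the task of estimation. A reader who follows it literally can reach a p-value and an HR that answer different questions.

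Calendar year is tied to treatment by design. Treated children have recent onset, and controls come from a long-running registry. If prognosis improved over time, for example through better supportive care, an unadjusted test would credit part of that to guanabenz. If prognosis worsened on paper, for example through earlier detection of decline, the bias would run the other way. The sponsor evidently thinks calendar year matters, because it is in the Cox model and in the mixed models for the HUI scores.

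The trial is open-label with historical controls and has one primary efficacy endpoint. If the two results disagree, the choice between them would be made after both are known.

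**Working it through.** **1. What each element of the plan adjusts for**

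| Element | Calendar year of onset | Stated role |
|---|---|---|
| Opening sentence of 6.3 | adjusted | defines the primary comparison |
| Matching (6.3) | not listed | builds the control set |
| Kaplan-Meier and log-rank (6.3) | no term or stratum | the only named test |
| Cox model (6.3) | covariate | effect size |
| Significance rule (4.1) | silent | one-sided p < 0.05, test not named |

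**2. Onset years of the treated group.** Inclusion was expected to start on 31 May 2021 (1.4) and ended on 31 May 2024 (3.6). Maximum disease duration is 8 years (5.2). The earliest onset is thus about 2021 − 8 = 2013 and the latest about 2024. The SAP gives no onset range for the controls.

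**3. Size of the possible bias.** The SAP has no figure on this point to reproduce: its power example in 3.3 uses a McNemar test on a two-year proportion. A null-drug simulation was run with these inputs:
- From the SAP: 30 treated (example in 3.3), 60 controls (1:2), one-sided 0.05, and 60% event-free at 2 years (middle of the 50–70% in 3.3), so hazard = −ln(0.6)/2 = 0.255 per year.
- Assumed: exponential times; follow-up uniform on 1–4 years in both groups; treated onset uniform on 2015–2023; three control onset ranges; hazard multiplied by a drift HR per later decade of onset; matched-set clustering ignored; 3000 runs per setting.

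Share of runs declaring benefit with the unadjusted log-rank:

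| Drift HR per decade | Controls 1998–2018 | 2005–2018 | 2010–2020 |
|---|---|---|---|
| 1.0 | 0.05 | 0.04 | 0.05 |
| 0.9 | 0.09 | 0.06 | 0.07 |
| 0.8 | 0.17 | 0.11 | 0.08 |
| 0.7 | 0.28 | 0.19 | 0.11 |

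The Wald test of treatment in the Cox model with onset year gave 0.04–0.06 in every cell.

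**4. Check by formula.** Mean treated onset is 2019 and mean control onset is 2008, 2011.5 or 2015, so the gaps are 11, 7.5 and 4 years. The spurious HR is drift^(gap/10), and rejection ≈ Φ(|ln HR| × √(D × 2/9) − 1.645). With D ≈ 39 events, √(39 × 2/9) = 2.94.
- Drift 0.8, gap 11: HR = 0.8^1.1 = 0.78; rejection ≈ 0.18 (simulated 0.17).
- Drift 0.7, gap 4: HR = 0.7^0.4 = 0.87; rejection ≈ 0.11 (simulated 0.11).

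**5. Sensitivity to the endpoint.** The 60% refers to being alive and walking without support, whereas the primary endpoint is loss of walking with support (6.1). If 80% were event-free at 2 years (assumed), D falls to about 20 and √(20 × 2/9) = 2.11. Across gaps of 4 to 11 years the formula then gives about 6–8% at drift 0.9 and 9–21% at drift 0.7. The inflation is smaller but does not vanish.

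**6. Cost of adjusting.** With an assumed true HR of 0.43 and no drift, power was 46% for the adjusted Cox test against 69% for the log-rank (controls 1998–2018), and 53% against 67% (controls 2010–2020).

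**The case against.** The stronger reading is that the log-rank is the deciding test and that twenty years of drift enter it directly. A reader might infer both, but the SAP supports neither. It never says the log-rank decides: the adjusted Cox model stands under the same primary-analysis heading, and the opening sentence of 6.3 could be taken to mean that this model governs. Twenty years is the registry's data-collection span, not the onset span of the matched controls. Section 5.2 already narrows the control periods, and 6.3 leaves room for more matching variables. No drift rate or direction is given, and with no drift the log-rank holds its level. All of this stands.

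It is also fair that a log-rank can be stratified by onset period, so the method itself is not the obstacle; the text simply does not stratify. And 3.3 says the sample size does not rest on formal testing and aims at preliminary assessment. But 3.4 and 4.1 still set a superiority framework with a significance threshold, so a deciding test is needed.

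These points do not remove the gap. The restriction in 5.2 has no calendar limits and may refer to disease stage, and an option to add matching variables is not a commitment. The sensitivity analyses in 6.5 vary matching ratios, weights and model form, not onset-year overlap. Onset year is not among the baseline characteristics in 5.5.

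**Conclusion.** The point holds as an inconsistency and an open decision rule. Section 6.3 promises adjustment for calendar year and names a test without it, and 4.1 does not say which p-value is judged. Any calendar drift remaining among the selected controls would bias the log-rank p-value, which could then disagree with the adjusted HR.

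The size is conditional. For assumed drift HRs of 0.9 to 0.7 per decade, rejection under a null drug runs from about 6–9% to 11–28% instead of 5%, as assumed control onset varies over the ranges tried. The event rate is borrowed from walking without support, and equal follow-up in both groups is assumed. These figures show what the ambiguity could cost; they do not forecast the bias in this trial.

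**What to change.** In 4.1 and 6.3, name one deciding test: the one-sided test of the treatment term in the Cox model adjusted for calendar year of onset, with variance clustered on matched set. State that the unadjusted log-rank and Kaplan-Meier curves are supportive. This carries out the adjustment 6.3 already promises and takes the p-value, HR and interval from the same model.

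Report the distribution and overlap of onset years in the two groups, and state the calendar limits behind 5.2. Add a sensitivity analysis restricted to overlapping onset years, because where the groups do not overlap the adjusted coefficient extrapolates the trend. A mandatory onset-year caliper is not asked for: whether enough controls would remain is unknown.

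The change is to SAP wording plus one table and one sensitivity analysis. The real cost is power for the deciding test when onset year and treatment are strongly correlated, as in the last step of the working. The HR and confidence interval the SAP already plans to report carry that loss of precision.
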